8.3 POPULATIONS FOR ANALYSES

All enrolled subjects will be included for analyses.

8.4 STATISTICAL ANALYSES

8.4.1 GENERAL APPROACH

The biomarkers that will be qualified and quantified in the urine include Cystatin C, Kidney Injury Molecule-1 (KIM-1), Neutrophil gelatinase-associated lipocalin (NGAL), Beta-2-microglobulin, Microalbumin urine, spot creatinine, total protein, and glycosaminoglycans.

8.4.2 ANALYSIS OF THE PRIMARY ENDPOINT(S)

Abundance of each kidney injury biomarker for each laser will be analyzed using the Kruskal-Wallis statistical test. Multiple multivariate regression will also be used to control for stone size, operative time, and other potential confounders.

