8.2 SAMPLE SIZE DETERMINATION

A sample size of 108 patients will be accrued locally. We are enrolling 108 patients to allow for any potential exclusions due to failure to follow up or for patients who were not stented.

A study by Fahmy et al. prospectively evaluated urinary Kidney Injury Marker-1 (uKIM-1) levels in patients undergoing kidney stone surgery to compare the effect of Extracorporeal Shockwave Lithotripsy (ESWL) and Ureteroscopy/Laser Lithotripsy (URS) on biomarkers of renal damage¹. In this study, the 50 patients in the ESWL arm had a mean preoperative uKIM-1 of 5.78ng/mL (SE=0.8) and the 10 patients in the URS arm similarly had a mean preoperative uKIM-1 of 5.78ng/mL (SE=2.0). Two hours post operatively, the ESWL group had a mean uKIM1 of 10.14ng/mL (SE=1.4) and the URS group had a uKIM-1 of 5.49ng/mL (SE 0.7, SD=2.21). Another study by Timmeren et al evaluated uKIM1 in 11 health controls and 53 patients with varying degrees of kidney disease and found a -0.37 correlation ($p=0.016$) between uKIM-1 levels and eGFR.² That is, a 1ng/mL rise in uKIM1 correlated to a 0.37mL/min decline in eGFR. The purpose of our statistical analysis is to evaluate for non-inferiority of the two laser modalities in regard to occult kidney damage. Given that kidney stone disease is a recurrent illness often requiring multiple surgical interventions over the course of a patient's lifetime, we defined non-inferiority as producing a change in eGFR 1mg/mL. With an allocation ratio of 1:1, 99% power, non-inferiority limit of 40%, and alpha of 5%, using the noninferiority power calculation, our sample size is 49 patients in each study arm for 98 patients in total (~100). Based on these calculations and factoring in a 10% dropout rate, we seek to enroll 108 total patients.

Power Calculation References

2. van Timmeren MM, van den Heuvel MC, Bailly V, Bakker SJ, van Goor H, Stegeman CA. Tubular kidney injury molecule-1 (KIM-1) in human renal disease. *The Journal of pathology*. 2007;212(2):209-217.

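### Section 8.2 sizes the trial for non-inferiority, but the objective, endpoint and primary analysis concern difference, and no analysis is tied to a margin

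*Combined protocol and SAP*

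**What the plan says.** Section 8.2 states the aim of the analysis: "The purpose of our statistical analysis is to evaluate for non-inferiority of the two laser modalities in regard to occult kidney damage". The sample size follows from it: "With an allocation ratio of 1:1, 99% power, non-inferiority limit of 40%, and alpha of 5%, using the noninferiority power calculation", giving "our sample size is 49 patients in each study arm for 98 patients in total". The same section also defines the limit on another scale: "we defined non-inferiority as producing a change in eGFR 1mg/mL". The bridge from uKIM-1 to eGFR is a cited study that "found a -0.37 correlation", which the section then reads as "a 1ng/mL rise in uKIM1 correlated to a 0.37mL/min decline in eGFR".

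The synopsis and the Objectives and Endpoints table put the aim differently. The primary objective is whether laser type predicts differences in the biomarkers, and the primary endpoint is an association between laser type and renal damage.

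Sections 8.1 and 8.4.2 give the same primary analysis: "Abundance of each kidney injury biomarker for each laser will be analyzed using the Kruskal-Wallis statistical test". They add: "Multiple multivariate regression will also be used to control for stone size, operative time, and other potential confounders". Section 8.1 is headed as statistical hypotheses but states none.

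**The concern.** A Kruskal-Wallis test asks whether two distributions differ. Non-inferiority asks whether one laser is worse than a named reference by less than a set amount, and it is decided by comparing a confidence bound with that amount. Section 8.2 counts patients for the second question; Section 8.4.2 answers the first. The regression could produce a laser effect with a confidence limit, but nothing says that it will be read against a margin.

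Followed literally, the plan gives a no-difference p-value for each biomarker and no rule for turning any of them into the conclusion named in 8.2. A non-significant result could then be reported as non-inferiority, and a significant but small difference could be reported as a failure. If the choice of hypothesis is made after the assays are read, it is post hoc.

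**Working it through.** **The texts side by side.** Objective and endpoint: difference or association. Sections 8.1 and 8.4.2: a difference test per biomarker. These agree with each other. Section 8.2 alone speaks of non-inferiority. It names no reference laser and no sidedness for the 5% alpha. It gives two limits, 40% and an eGFR change of 1, without linking them to each other or to the analysis.

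**Can 49 per arm be reproduced?** Inputs from Section 8.2: post-operative URS mean 5.49 ng/mL, SD 2.21 (0.7 × √10), power 99%, allocation 1:1. Formula, with no true difference: n per arm = 2 × ((z_alpha + z_0.99) × SD / margin)², where z_0.99 = 2.326 and z_alpha = 1.645 (one-sided 5%) or 1.960 (one-sided 2.5%).

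| Margin (ng/mL) | One-sided 5% | One-sided 2.5% |
|---|---|---|
| 0.40 × 5.49 = 2.196 (base assumed) | 31.9 → 32 | 37.2 → 38 |
| 1 / 0.37 = 2.70 (reads the correlation as a slope) | 21.1 → 22 | 24.6 → 25 |

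Neither margin gives 49. Working backwards at SD 2.21, 49 per arm fits a margin of (1.645 + 2.326) × 2.21 × √(2/49) = 1.77 ng/mL (32% of 5.49), or 1.91 ng/mL (35%) with 1.960.

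A binary formula with a 40-point limit comes close. At 50% in each arm and one-sided 5%, 2 × 0.5 × 0.5 × (1.645 + 2.326)² / 0.40² = 49.3. At 30% and one-sided 2.5% it gives 48.2. The documents state no binary endpoint or event rate, so this is only a possible origin.

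**How the two questions can diverge.** Illustration by simulation: 40,000 trials per scenario, normal data, 49 per arm, Kruskal-Wallis at two-sided 5%, non-inferiority if the pooled-t one-sided 95% upper bound is below 2.196. The margin and the true excess are assumptions.

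- SD 2.21, true excess 1.0: Kruskal-Wallis significant 58%, non-inferiority met 85%, both 43%. So 42.8 / 58.2 = 74% of the significant trials would still be non-inferior.
- SD 2.21, non-significant result: for a t-type test the difference is below 1.985 standard errors, so the upper bound is below (1.985 + 1.661) × √(2/49) × SD = 0.737 × 2.21 = 1.63 ng/mL, which is under 2.196.
- SD 6.32 (assumption: pre-operative URS SE 2.0 × √10), no true difference: about 45% of trials are non-significant and still fail the margin. Here the same cap is 0.737 × 6.32 = 4.66 ng/mL, well above 2.196.

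**The case against.** The strongest reply is that the analysis is not wrong. Objective, endpoint and Kruskal-Wallis test are consistent, and only 8.2 departs from them. That stands: this is a conflict caused by 8.2, not an unsuitable test.

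A second reply is that the feared misreading is harmless at the printed SD. A reader might infer that a non-significant p-value never says anything about non-inferiority here. The inputs do not support so strong a reading: at SD 2.21 and the assumed margin, non-significance would in practice place the upper bound below 2.196. The discordance left at that SD, significant yet non-inferior, errs on the cautious side for a safety claim. The false-reassurance risk therefore depends on a larger SD. The 6.32 comes from pre-operative values in 10 patients, and normal data with that SD would put about 19% of values below zero, so it is a sensitivity case and not an estimate.

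A third reply is that the margin of 2.196 is itself assumed. That is correct, and it is part of the problem: the plan gives no base from which to derive a better one.

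Nor do the documents show that the trial is too small. At SD 2.21, 49 per arm exceeds the number needed for either candidate margin.

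**Conclusion.** The concern holds and must be fixed. Section 8.2 declares a non-inferiority purpose that no prespecified analysis can deliver, because no margin on the analysed scale, reference laser or decision rule exists. This rests on the text alone and needs no assumption.

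The figures only show its size. The non-reproduction of 49 holds for both candidate uKIM-1 margins at SD 2.21. The 43% depends on the assumed margin and a chosen excess of 1.0 ng/mL; the 45% also depends on the larger assumed SD and on normal data. The conclusion does not extend to calling Kruskal-Wallis the wrong test for the stated objective.

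**What to change.** Make Sections 8.1, 8.2 and 8.4.2 state one aim. The sponsor can choose either option.

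**Option A: keep non-inferiority.**
- Name one marker (uKIM-1, which was used for sizing), one of the two scheduled post-operative time points, and a reference laser. If a symmetric claim is meant, state two-sided equivalence instead.
- Give one margin with its base and scale, reconciled with the eGFR definition. The 0.37 is reported as a correlation and cannot serve as a slope.
- Conclude non-inferiority only if the confidence bound for the between-laser difference is below that margin, and state whether the 5% alpha is one-sided.
- Take the bound from an unadjusted model, or from one adjusted only for pre-operative variables such as baseline uKIM-1 and stone size. The planned regression adjusts for operative time, which arises after randomisation and may be affected by the laser; adjusting for it could remove part of the effect.
- Restate the sample size or power for that margin and SD.
- Keep Kruskal-Wallis as supportive, and state that p > 0.05 is not evidence of non-inferiority.

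**Option B: drop non-inferiority.** Remove it from 8.2, keep 8.4.2 as the difference test, and restate what 49 per arm can detect. At 80% power and two-sided 5%, (1.96 + 0.8416) × SD × √(2/49) gives about 1.25 ng/mL at SD 2.21 and about 3.6 ng/mL at SD 6.32.

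**Cost.** Wording and a little analysis; the change itself needs no extra samples or patients. Under Option A one marker and one time point take precedence and the others become supportive. The stated 99% power may also have to be restated: with the assumed margin of 2.196, one-sided 5% and no true difference, 49 per arm gives above 99% at SD 2.21 but about 53% at SD 6.32.

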1.3 SCHEDULE OF ACTIVITIES

After randomization, the patient will undergo URS using either the Thulium or Hol:YAG laser. Both lasers are used as part of the standard of care and are used interchangeably. At the beginning of all procedures, the surgeon will empty the bladder and collect a 2 mL sample of urine that will serve as the “Preoperative Urine Sample”. It is the standard of care to collect urine at the beginning of the surgery to send to pathology. The only deviation is that a portion of the urine will be for research. One hour following the end of the procedure, a member of [name] research team will collect a second 2 mL sample of urine that will serve as the “Immediate Post-Op Urine Sample”. This will be collected using the catheter that was placed during surgery. If no catheter was placedb the patient will provide the urine sample.

After collection, the samples will be subsequently frozen in a freezer at -80 °C freezer operated by the pathology department at Mount Sinai West hospital.

A third and final sample of urine will be collected at the patients’ 10-day follow up appointment for stent removal which will serve as the “Follow-up Urine Sample”. To standardize the duration in which the last urine samples are collected, only patients who have been stented will be included in the study, as standard of care for stent removal is ten days. Upon receiving the third and final specimen 10 days postoperatively, the subject’s enrollment will be considered complete. All procedures and appointments are the standard of care.

After sufficient patient enrollment and specimen collection, all the samples will be analyzed for kidney and urothelial injury biomarkers using urinary assays (ELISA, CLIA, etc.). The biomarkers that will be qualified and quantified in the urine include Cystatin C, Kidney Injury Molecule-1 (KIM-1), Neutrophil gelatinase-associated lipocalin (NGAL), Beta-2-microglobulin, Microalbumin urine, spot creatinine, total protein, and glycosaminoglycans.

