8 STATISTICAL CONSIDERATIONS

8.1 STATISTICAL HYPOTHESES

After sufficient patient enrollment and specimen collection, all the samples will be analyzed for kidney and urothelial injury biomarkers using urinary assays (ELISA, CLIA, etc.). The biomarkers that will be qualified and quantified in the urine include Cystatin C, Kidney Injury Molecule-1 (KIM-1), Neutrophil gelatinase-associated lipocalin (NGAL), Beta-2-microglobulin, Microalbumin urine, spot creatinine, total protein, and glycosaminoglycans.

Abundance of each kidney injury biomarker for each laser will be analyzed using the Kruskal-Wallis statistical test. Multiple multivariate regression will also be used to control for stone size, operative time, and other potential confounders.

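### The primary analysis names no primary marker, time point, deciding analysis or multiplicity rule, and its difference test cannot show the non-inferiority that section 8.2 gives as the purpose

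*Combined protocol and SAP*

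**What the plan says.** The primary analysis in section 8.4.2, repeated in 8.1, is two sentences. The first is "Abundance of each kidney injury biomarker for each laser will be analyzed using the Kruskal-Wallis statistical test". The second is "Multiple multivariate regression will also be used to control for stone size, operative time, and other potential confounders".

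Section 8.4.1 lists eight analytes: cystatin C, KIM-1, NGAL, beta-2-microglobulin, and "Microalbumin urine, spot creatinine, total protein, and glycosaminoglycans". Spot creatinine is given no separate role. The endpoint table frames the comparison in concentrations and names no marker or time.

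Section 1.3 schedules three urine samples: at the start of the procedure, then "One hour following the end of the procedure", then at the 10-day visit. Section 8.1 says "all the samples will be analyzed for kidney and urothelial injury biomarkers using urinary assays", but not which sample is compared between lasers. Section 2.2 says markers are measured before and after surgery, without defining a change score or a baseline covariate.

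Section 8.2 states: "The purpose of our statistical analysis is to evaluate for non-inferiority of the two laser modalities in regard to occult kidney damage". It uses KIM-1 figures only, at 99% power and one 5% alpha whose sidedness is not given. It states the limit in two ways: 40%, and an eGFR change of 1.

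**The concern.** The aim in 8.2 and the test in 8.4.2 do not match. A Kruskal-Wallis p-value above 0.05 means only that no difference was detected. It does not bound how much worse one laser could be. As written, no result of the primary analysis would answer the non-inferiority question.

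The plan also leaves open which of many results answers the primary question. There are seven or eight markers, two post-operative samples and two unranked analyses, against a single 5% alpha. The two analyses need not agree: the regression conditions on operative time, which is observed after randomisation and could itself depend on the laser. A chance difference in one marker could be reported as a laser effect.

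Finally, the preoperative sample is collected but not named in the analysis, so a gain in precision may be lost.

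**Working it through.** **1. What 8.2 fixes.** Inputs from 8.2: "the URS group had a uKIM-1 of 5.49ng/mL (SE 0.7, SD=2.21"), n = 10, and a preoperative URS mean of 5.78 ng/mL (SE 2.0). The SD reproduces: 0.7 × √10 = 2.21. The two statements of the limit give different KIM-1 margins:

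- 40% of 5.49 = 2.20 ng/mL
- 40% of 5.78 = 2.31 ng/mL
- eGFR change of 1, by the plan's own conversion: 1/0.37 = 2.70 ng/mL

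With n per arm = 2 × SD² × (z₀.₉₅ + z₀.₉₉)² / margin², SD 2.21 and one-sided 5%, these give 32, 29 and 22 per arm. The stated figure is 49. That mismatch is a separate matter. Here it shows only that 8.2 does not fix a margin that 8.4.2 could use.

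**2. Chance of at least one p<0.05 when the lasers do not differ.** This assumes that any one such result counts. For k independent tests the chance is 1 − 0.95^k:

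- k = 7 (one time point, creatinine not tested): 1 − 0.698 = 30.2%
- k = 8 (creatinine tested): 1 − 0.663 = 33.7%
- k = 14 (seven markers, both post-operative samples): 1 − 0.488 = 51.2%

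Markers from one urine sample are likely to be correlated. A simulation with equally correlated normal test statistics (400,000 draws, two-sided 5%) gives:

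| Tests | correlation 0.3 | 0.5 | 0.7 |
|---|---|---|---|
| 7 | 27.2% | 23.0% | 17.9% |
| 8 | 29.9% | 25.1% | 19.2% |
| 14 | 43.8% | 34.7% | 25.0% |

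The correlations are assumptions; the documents give none.

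**3. Cost of leaving out the preoperative value.** Adjusting for baseline multiplies the variance of the laser comparison by 1 − r², where r is the pre/post correlation (assumed):

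- r = 0.3: 0.91
- r = 0.5: 0.75
- r = 0.7: 0.51

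**4. What the cited KIM-1 data say about timing.** The URS change at 2 hours is 5.49 − 5.78 = −0.29 ng/mL. Its SE is √(2.0² + 0.7² − 2r × 2.0 × 0.7), which is 2.12 at r = 0 and 1.30 at r = 1. With t(9) = 2.262, the 95% interval is −5.08 to 4.50 or −3.23 to 2.65. The data neither show nor exclude a rise. Two hours also matches neither sampling time in section 1.3.

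**The case against.** **The error rates depend on a rule the plan does not state.** This stands. A reader might infer that the trial has a 30% or 51% false-positive rate, but the documents do not say that any one p<0.05 would count. If all markers had to pass, error would not inflate and power would fall instead. These rates also concern falsely claiming a difference, which is not the error that matters most for non-inferiority. They show what the omission allows.

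**Multivariate regression may mean one joint model of all markers.** This stands in part. A joint laser test would hold its level: a simulation with seven markers and 49 per arm rejected 4-5% of the time under no effect. But no joint test is stated, and the per-marker Kruskal-Wallis tests would remain. Because the term is ambiguous, the regression is not counted here as a second test per marker.

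**The unnamed confounders could include the preoperative value.** They could, so the fair statement is that its use is not specified. It would be too strong to infer that it will be ignored.

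**Urine dilution might be thought to bias the laser comparison.** The documents do not support that. Laser is randomised, so dilution mainly adds noise. Bias is possible for non-randomised factors such as pressurised irrigation (section 8.4.3), but the documents do not allow its size to be computed.

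**This is a single-practice biomarker study that may be meant as exploratory.** The documents do not say so. They state a randomised primary objective, a non-inferiority purpose and 99% power. If exploration is intended, the plan should say so and drop the non-inferiority claim.

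**Conclusion.** The point holds as an omission in the primary analysis that should be put right before assays are run. It has two firm parts, which rest on the text alone: nothing says which marker, time or analysis decides, and the test named cannot establish the stated purpose.

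The size is conditional. If any one p<0.05 counts, the false-positive chance is 18-30% for seven markers at one time, and 25-51% if both post-operative samples are tested, for assumed correlations from 0.7 down to 0. The loss from not using the preoperative value is one of precision only, and depends on an assumed pre/post correlation.

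A reader might infer from the cited figures that KIM-1 does not rise after ureteroscopy and so cannot serve as the primary marker. Ten patients and an interval spanning several ng/mL either side of zero do not support that. They show only that the time point needs its own justification.

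**What to change.** Before assays are run, amend 8.2, 8.4.1, 8.4.2 and 8.4.3:

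- Name one primary marker at one post-operative time point and justify both. KIM-1 is the natural candidate, since 8.2 plans on it alone.
- Make one analysis decisive: regression of the log marker on laser, adjusted for the log preoperative value of the same marker. Name any further covariate in advance. Keep Kruskal-Wallis as a sensitivity analysis.
- Handle dilution the same way before and after surgery, for example with creatinine-indexed values at both times. Use spot creatinine for this, not as a tested injury marker.
- Judge non-inferiority by comparing the confidence bound for the laser effect with a single margin on the analysed scale. State the sidedness, and whether one laser is the reference or both directions must be shown. Apply the 5% alpha to this comparison only, and restate power.
- Treat the other markers as secondary with a multiplicity adjustment such as Holm, or as exploratory. Label the other time point and the operative-factor analyses exploratory.

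Cost: no new samples or assays, because the preoperative urine and creatinine are already planned. It is more than a wording change. Section 8.2 gives no usable SD or single margin on a log, dilution-corrected scale, so both must be derived and the sample size checked again. Fewer confirmatory claims will be possible.

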8.4.3 ANALYSIS OF THE SECONDARY ENDPOINT(S)

Operative time, patient positioning, use of pressurized irrigation, and use of a ureteral access sheath) will be analyzed with Kruskal-Wallis statistical tests and multivariate regression to predict differences in levels of renal-damage associated biomarkers.

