2.3.3 ASSESSMENT OF POTENTIAL RISKS AND BENEFITS

Other than the extremely small risk of compromising protected health information, we do not foresee any risks or benefits to participants in this study. The extent of participation for each subject involves collection of three perioperative urine samples (collected via cystoscope, Foley catheter, or clean void). No invasive procedure will be performed to collect the samples (for example, a Foley catheter will not be placed solely for the purpose of collecting a urine sample for this study).

OBJECTIVES AND ENDPOINTS

OBJECTIVES	ENDPOINTS	JUSTIFICATION FOR ENDPOINTS	PUTATIVE MECHANISMS OF ACTION
Primary			

OBJECTIVES	ENDPOINTS	JUSTIFICATION FOR ENDPOINTS	PUTATIVE MECHANISMS OF ACTION
1) To determine if during ureteroscopic laser lithotripsy, laser type (Ho:Yag Moses 2.0 vs Thulium Fiber Laser) predicts differences in renal-damage associated biomarkers	1) Determination of association between type of laser used during URS and degree of renal damage (as measured by urinary biomarkers).	Quantification of the concentrations of specific urinary biomarkers will allow us to compare the relative tissue damage caused by each laser type.	N/A
Secondary			
To determine if any additional operative factors (i.e. operative time, patient positioning, use of pressurized irrigation, use of a ureteral access sheath) predict differences in levels of renal-damage associated biomarkers.	The secondary endpoint will be determination of association between additional operative variables (see secondary objective) and renal damage during URS.	Quantification of the concentrations of specific urinary biomarkers will allow us to compare the relative tissue damage caused by different variables during URS.	N/A

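### Section 8.4.3 applies Kruskal-Wallis to operative time, a continuous predictor the test does not suit; the defect is confined to that part of one secondary analysis

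*Combined protocol and SAP*

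**What the plan says.** The secondary objective, in the Objectives and Endpoints table, is "To determine if any additional operative factors (i.e. operative time, patient positioning, use of pressurized irrigation, use of a ureteral access sheath) predict differences", the outcome being the renal-damage biomarkers. Operative time is the first factor named.

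Section 8.4.3 is the whole analysis plan for that objective. Its single sentence opens "Operative time, patient positioning, use of pressurized irrigation, and use of a ureteral access sheath) will be analyzed with Kruskal-Wallis statistical tests". The rest of that sentence attaches a second method to the same list: "and multivariate regression to predict differences in levels of renal-damage associated biomarkers". Four factors are thus pooled in one list and two methods are attached to the list. The other three factors read as categorical.

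Section 8.4.2, on the primary endpoint, also uses operative time, there as an adjustment variable: "Multiple multivariate regression will also be used to control for stone size, operative time, and other potential confounders".

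Neither document part gives categories or a cut-point for operative time, names a correlation or trend test, or says whether it enters the regression as continuous. Section 8.2 sizes the trial for the laser comparison only ("our sample size is 49 patients in each study arm for 98 patients in total (~100"). No power is claimed for any secondary factor.

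**The concern.** Kruskal-Wallis asks whether a rank distribution differs between a small number of groups. Operative time is continuous, so an analyst applying the sentence literally has two choices, and neither is good.

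- **Leave the times ungrouped.** Nearly every patient becomes a group of one, and the test says little or nothing about the biomarker.
- **Group the times.** The test then runs, but it discards the ordering within groups (and, with three or more groups, the ordering between them). Someone must also choose the cut. Section 8.4.1 lists eight urinary measures, so a cut left open could be tried against each of them.

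What is at stake is the unadjusted result for the first-named secondary factor. It could be uninformative or dependent on the cut, and could sit beside a regression result that disagrees with it, with no rule for which is to be believed.

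**Working it through.** The plan states no power or effect size for this analysis, so there is no figure of its own to reproduce. Two checks apply.

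**1. Ungrouped times (algebra, no assumed effect)**

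Input: N = 98, from section 8.2.

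H = 12/(N(N+1)) × Σ(R²/n) - 3(N+1), where R is the rank sum and n the size of each group.

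If all times differ, every n = 1 and ΣR² is the sum of squared ranks, N(N+1)(2N+1)/6. Then

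H = 2(2N+1) - 3(N+1) = N - 1.

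With N = 98:
- ΣR² = 98 × 99 × 197/6 = 318,549
- 12/(98 × 99) × 318,549 = 394
- H = 394 - 3 × 99 = 97, on 97 degrees of freedom
- P(chi-square with 97 df > 97) = 0.481

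The biomarker values do not enter. With all 108 enrolled patients the same algebra gives H = 107 on 107 df.

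**2. Power when times are recorded coarsely or grouped (simulation)**

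Inputs from the documents: N = 98; alpha 5%, which section 8.2 states for the laser comparison without sidedness, taken here as two-sided.

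Assumed, not in the documents: bivariate normal data; correlation between operative time and biomarker of 0.2, 0.3 or 0.4; operative time with mean 60 and SD 20 minutes. The mean and SD affect essentially only the rows with rounded times.

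| Method | 0.2 | 0.3 | 0.4 |
|---|---|---|---|
| Kruskal-Wallis, whole-minute times | 0.3% | 0.5% | 1.8% |
| Kruskal-Wallis, 5-minute bins | 7% | 22% | 49% |
| Kruskal-Wallis, quartiles | 27% | 60% | 90% |
| Kruskal-Wallis, median split | 33% | 65% | 90% |
| Spearman correlation | 46% | 83% | 98% |
| Linear regression, continuous time | 50% | 85% | 98% |

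A repeat with 1,500 simulated trials per setting agrees within 3 points. The simulation error at that size is at most √(0.25/1,500) = 1.3 points (one standard error).

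Power lost against Spearman at 0.2, 0.3 and 0.4:
- median split: 46 - 33 = 13, 83 - 65 = 18, 98 - 90 = 8 points
- quartiles: 46 - 27 = 19, 83 - 60 = 23, 98 - 90 = 8 points
- 5-minute bins: 46 - 7 = 39, 83 - 22 = 61, 98 - 49 = 49 points

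At an assumed correlation of 0.5 the methods draw closer: about 82% for 5-minute bins and 99% for a median split, against more than 99% for Spearman. Whole-minute times still give only about 4%.

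**The case against.** The strongest reply is that the sentence does not stop at Kruskal-Wallis. It lists four factors and two methods, and a sensible analyst would use each method where it fits: the rank test for positioning, irrigation and sheath use, and regression for operative time. Section 8.4.2 already uses operative time in a regression. This stands, and it sets the limit of the point: operative time has a workable method in the plan.

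The reply also notes that nobody would report a test on 98 groups of one. The value 0.48 comes from applying the chi-square approximation to groups of size 1, would look odd at once, and would lead the analyst to group the times or rely on the regression. That is probably right. A reader might infer that the trial will report a false absence of association for operative time. The documents do not support this: they do not say the times are to be left ungrouped, a regression estimate is planned alongside, and a null result would be false only if an association exists. Nor is near-zero power general. It holds for distinct or whole-minute times, not for 5-minute bins or broader groups.

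Finally, the power figures rest on correlations and a spread of times that are assumed, for a secondary factor with no powered hypothesis. That is also fair, and is why a range is shown.

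What survives is narrower. The text assigns the test to operative time, does not divide the methods between the factors, and sets no cut-point. Grouping, the only way to make the test usable, costs power at every correlation from 0.2 to 0.4 and leaves a choice to be made after the data are seen.

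**Conclusion.** Wrong as written, and minor. Kruskal-Wallis does not suit operative time. Ungrouped distinct times give a fixed result, which is algebra and needs no assumption. Grouped into halves or quartiles, the test loses roughly 8 to 23 points of power against Spearman for correlations of 0.2 to 0.4. That range rests on N = 98, a two-sided 5% level and normal data, and the correlations are not in the documents. The figures for whole-minute and 5-minute times rest in addition on an assumed SD of 20 minutes.

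The defect is limited to the Kruskal-Wallis part of one secondary analysis. It does not show that the operative-time question is unanswerable, because the regression in the same sentence can take time as continuous. It does not touch the laser comparison, where operative time is only a regression covariate.

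**What to change.** Amend section 8.4.3 to:

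- limit Kruskal-Wallis (the rank-sum test where there are two groups) to positioning, pressurised irrigation and access-sheath use;
- analyse operative time as continuous, with Spearman correlation as the unadjusted test and a continuous term in the regression already planned;
- state that, if operative-time categories are also shown, the cut-points are set before the data are seen.

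This defect requires no change of outcome scale and no further covariates. The cost is a sentence or two in the analysis section, with no new data and no change to sample size or conduct.
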